# BACKGROUND

## Rationale and research questions

BLT Pilot aims to test the feasibility of conducting a controlled clinical trial designed to evaluate the effectiveness and cost-effectiveness of minimal and enhanced “encouragement” to initiation and regular use BLT for treatment of an incident unipolar depressive episode among adult members of the KPNW medical plan. Encouragement includes motivational interviewing, education, and tools for using BLT with high adherence.

Our primary clinical outcome is the PHQ-9 at post-acute treatment (2 months follow-up). Our primary process outcomes are initiation of BLT therapy and adherence to best BLT practices.

## Hypotheses

While this is a pilot study and not powered to assess intervention effects, we hypothesize that the combined intervention (minimal + enhanced encouragement arms) will have larger reductions in PHQ-9 at post-acute treatment than the TAU control arm; and that enhanced encouragement will have larger reductions in PHQ-9 at post-acute treatment than minimal encouragement.

## Abbreviations

BLT, bright light therapy; SD, standard deviation; ITT, intention-to-treat; CEA, cost effectiveness analysis; TAU, treatment as usual; LB, light box; PHQ-9, patient health questionnaire 9-item version; HLM, hierarchical linear models; EHR, Electronic Health Record; SE, Standard Error; ISI, insomnia severity index; MI, motivational interviewing; ES, effect size.

## Preliminary data evaluation

Before any analyses, we will conduct procedures to assess data quality and completeness and will evaluate missing data patterns. In order to maximize analytic team efficiency, we will audit data from the initiation of data collection. Careful descriptive analyses (e.g., mean, SD, range, skewness) will be conducted for all study variables of interest. We will evaluate distributions to ensure that they meet the assumptions of planned analyses (below), including the detection of outliers (another potential indicator of entry error). As noted early, this proposed R34 pilot is underpowered to perform formal tests of effectiveness. However, we will conduct analyses as we would for a fully-powered, R01-funded project, both to demonstrate feasibility and to generate effect size estimates for the future, fully powered randomized trial—subject to the limits and cautions of using pilot data for this purpose (e.g., use with very wide confidence intervals)[1-3].

## Management of missing data

Data can be missing for many reasons, including entry errors, interviewer omissions, treatment refusal, acute medical illness, etc. Missing data is also a consequence of attrition, but we expect dropout from the study will be less than 10% at the 6-month follow-up assessment. To carry out the planned ITT analyses, we use multiple imputation methodology to account for missing data[4, 5]. These methods preserve the correlational structure among the study measures and incorporates the uncertainty inherent in replacing missing values, and as with other imputation procedures, they assume data are “missing at random” (MAR). We will create 10 imputed datasets, repeating outcome analyses across each replicate, and will use Rubin’s rules to produce adjusted estimates and statistics from which inferences will be drawn[6].

## Analysis of primary outcome

For our PHQ-9 primary outcome, we will test whether there are differences in score trajectories across time between arms with two-level hierarchical linear models (HLMs) in a growth curve framework[7-9]. The first level of the model will include time as a predictor, modeling within-person variation. The second level will include a dummy variable for arm (e.g., 1=TAU+BLT+AP or TAU+BLT, 0=TAU) as the predictor variable for both the random effects of the intercept and slope for time. A significant coefficient for arm on the time slope would indicate that there are different trajectories across time for BLT arms versus TAU. We will probe any significant arm x time interactions by graphing the simple-effects equations to determine whether the observed pattern is consistent with hypotheses. Compared to the Arm 1 TAU condition, a pattern in which the active arms (Arms 2 and 3) exhibit a greater PHQ-9 decrease over time supports the effectiveness of the intervention. However, recall this pilot is insufficiently powered to formally test intervention effects[1-3].

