A request for Waiver of Authorization is also requested for recruitment. During the first stage of the screening process, we will run an EHR case-finding program to generate an initial outreach list of potentially eligible individuals. This initial case finding algorithm does not itself qualify individuals for the study, but merely generates a likely pool within which further screening is merited.

This waiver allows study staff to approach (via letter, email/the EHR patient portal, and subsequent phone call) likely interested and eligible individuals and offer them the study opportunity. The study could not complete the research without access to and use of PHI because it is not practical to recruit eligible individuals without pre-identifying using medical record information and contact information. It would be too costly and would un-duly burden the KP membership to receive invitations to every study. Only the minimum amount of PHI will be accessed to identify participants who are likely to meet the study eligibility criteria.

6. Study Procedures

Recruitment

Recruitment procedures are described in the earlier Recruitment Methods section.

Randomization

Participants will be randomized 1:1:1 to three conditions, stratified by gender (male vs. female + all non-CIS gender identities), age (median split; estimated as <46yrs vs >= 47yrs), and minority status (white non-Hispanic vs. all other races/ethnicities).

Monitoring for Safety

The target condition is depression, and the most likely emergent risks (and how we will monitor for these) are:

- Worsening depression, evaluated at each assessment with the PHQ-9 depression measure.
- Intentional self-harm, including suicidal thoughts and behavior. This will be evaluated at each assessment with the Columbia Suicide Severity Rating Scale (C-SSRS).
- Emergent bipolar disorder symptoms (a possible risk of triggered symptoms from lightbox use). This will be assessed at each follow up assessment with the 5-item Altman Self-Rating Mania Scale (ASRM).

Any increased risk evident from any of these measures, or other unexpected increased in other less common safety issues (e.g., threats to harm others) will be reviewed between the interviewing staff and [name], with a review of the relevant usual health care the individual is already receiving.

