## Moderation and mediation

In addition to primary outcome analyses we will conduct exploratory analyses of moderation using variables identified through previous research and clinical expertise, specifically indication of pharmacotherapy use (1=yes, 0=no), age (continuous), gender (1=female, 0=male), race and ethnicity (1=racial/ethnic minority, 0=non-Hispanic white), baseline PHQ-9 (1=clinically elevated, 0=below clinical range), and EHR indication of mental health comorbidities such as eating disorders, anxiety (1=comorbidity, 0=no comorbidity). Moderation will be indicated by a significant time x arm x moderator interaction in HLM.

We propose to conduct exploratory analyses of the BLT mediation pathway as the extent to which the relation between BLT and outcomes is mediated by changes in participants' 1) sleep (sleep diary and actigraphy, and ISI subjective sleep quality), 2) total physical activity, and 3) circadian timing and chronotype. For example, to evaluate the mediating effect of ISI sleep quality we will regress post-acute treatment ISI on baseline ISI and a randomization condition indicator; and we will regress follow-up PHQ-9 at post-acute treatment ISI and a randomization condition indicator. Using the product coefficients mediation approach, we will use the resulting regression coefficients and standard errors (SEs) to estimate the indirect effect[10-12]. Because SEs of the products of regression coefficients are not normal, we will use bias-corrected bootstrapping to estimate the SEs for the indirect effect.[12] We will use a similar approach for the MI pathway to test the mediating effect of participants' increased readiness to change on BLT adherence.

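### The primary PHQ-9 model omits the three stratification factors, which costs precision only to the extent that they predict change in PHQ-9

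*SAP*

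**What the plan says.** Protocol section 6, Randomization, allocates 1:1:1, "stratified by gender (male vs. female + all non-CIS gender identities), age (median split; estimated as <46yrs vs >= 47yrs), and minority status". Three two-level factors give eight strata. Block size and method of allocation within strata are not stated.

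The SAP, Analysis of primary outcome, has time at level 1. At level 2 it says: "The second level will include a dummy variable for arm", entering "as the predictor variable for both the random effects of the intercept and slope for time". No other level-2 term is named, and the protocol's Data Analysis section describes the same model. The term to be tested is identified: "A significant coefficient for arm on the time slope would indicate that there are different trajectories across time for BLT arms versus TAU". The SAP nowhere mentions that randomisation is stratified.

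The same characteristics return in the SAP under Moderation and mediation, for exploratory interaction tests only, coded as "age (continuous), gender (1=female, 0=male), race and ethnicity (1=racial/ethnic minority, 0=non-Hispanic white". Age is continuous there but split at randomisation. Gender is female versus male there, whereas randomisation groups women with all non-CIS identities. The race and ethnicity coding matches the stratum.

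Two further passages bear on the remedy. The SAP's Rationale and research questions says "Our primary clinical outcome is the PHQ-9 at post-acute treatment (2 months follow-up", which is a single-visit outcome rather than a slope. The SAP's Analysis of secondary outcomes calls the logistic and count models multivariable but lists no covariates.

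**The concern.** When allocation is balanced within strata, variation between strata largely drops out of the true sampling variance of the arm contrast. A model without the strata leaves that variation in its residual, so the estimated SE can exceed the true one. Intervals are then wider than they need be, and a nominal 5% test rejects less than 5% of the time.

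What is at stake is precision, not bias. The SAP intends the pilot's analyses to follow those of the later full trial and to supply effect estimates with intervals for planning it. With 90 randomised and 81 expected at six months, width that can be removed cheaply is worth removing, and a model that omits the strata would pass to the next trial as its template.

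**Working it through.** **1. The plan's own figures.** The documents give no SE, and no estimate of how well the strata predict PHQ-9. The nearest figures are the minimum detectable effects in the SAP's power section: d = 0.55 for single-arm contrasts and 0.39 for Arms 2 and 3 versus Arm 1 (80% power, two-sided 0.05, N = 81, autocorrelation 0.70).

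- Formula: d = (1.960 + 0.842) × f × √(1/n₁ + 1/n₂), with f = √(1 − 0.70²) = 0.714.
- 27 versus 27: 2.802 × 0.714 × 0.272 = 0.545, which agrees with 0.55.
- 54 versus 27: 2.802 × 0.714 × 0.236 = 0.472, which does not agree with 0.39. No variance factor tried gave both figures.

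That mismatch is a separate matter. The results below are ratios and do not depend on it.

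**2. Which stratum effects reach the tested term.** With complete data at months 0, 2, 4 and 6, the arm-by-time contrast is a comparison of per-person slopes. A constant added to all four of a person's scores leaves that person's slope unchanged. Stratum effects on level therefore cancel, and only stratum effects on slope remain.

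**3. Size when the strata do predict slope.** Let R² be the share of between-person variance in the estimated slope that the strata explain. This is an assumption, shown over a range that includes zero.

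- SE(adjusted) / SE(unadjusted) = √(1 − R²), so the unadjusted SE is wider by 1/√(1 − R²) − 1.
- If strata were exactly balanced across arms, the unadjusted test's type I error would be 2 × [1 − Φ(1.96/√(1 − R²))].

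The last column comes from a simulation of the pooled contrast: N = 90, eight strata, permuted blocks of 3, four visits, complete data, and two runs of 20,000 and 30,000 replicates per scenario. Block size, stratum prevalences and variance components were assumed.

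| Assumed slope R² | √(1 − R²) | Unadjusted SE wider by | Type I error, exact balance | Type I error, simulated |
|---|---|---|---|---|
| 0 (strata affect level strongly) | 1.000 | 0% | 5.0% | 5.0 to 5.1% |
| 0.02 | 0.990 | 1.0% | 4.8% | not run |
| 0.05 | 0.975 | 2.6% | 4.4% | 4.5 to 4.8% |
| 0.10 | 0.949 | 5.4% | 3.9% | 4.1 to 4.3% |

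The mean unadjusted SE divided by the true standard deviation of the estimate was 0.997 to 0.999 in the first row, 1.016 to 1.018 at R² = 0.05 and 1.035 to 1.047 at R² = 0.10.

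**4. Dependence on blocking.** A separate simulation at R² = 0.10 (12,000 replicates per case, stratum prevalences assumed) gave type I error of 3.8% with blocks of 3, 4.1% with blocks of 6 or 9, and 4.8% with unblocked allocation within strata. The Monte Carlo SE is about √(0.04 × 0.96/12,000) = 0.18 percentage points, so the block sizes are not clearly separated, but the unblocked case is. Without blocking, the unadjusted test is close to its nominal level and simply less precise than the adjusted one.

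**5. In practical units.** Adjustment is worth a sample of 90/(1 − R²): 91.8, 94.7 and 100 at R² = 0.02, 0.05 and 0.10, or about 2, 5 and 10 extra participants. At R² = 0.10 the stated 0.55 would become 0.55 × 0.949 = 0.522.

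**6. Which terms to add.** By step 2, strata on the intercept alone leave the SE of arm by time unchanged. Stratum-by-time terms are needed.

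**The case against.** A reader might infer that the error bars are too wide as a matter of fact, or that the design has been ignored in a way that undermines the analysis. The documents support neither. The tested coefficient is a slope contrast, level differences between strata do not reach it, and nothing in the protocol or SAP says that gender, age or minority status predicts change in PHQ-9. If they do not, there is no loss.

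It is also fair to say that any error is on the safe side: no bias and no excess of false positives. The SAP states that the pilot cannot formally test effects and that its effect sizes will be used only with wide intervals. Its planning example already spans d = 0.35 to 0.50, next to which a change of a few per cent in the SE is small. The type I figures depend on an allocation method that the protocol does not describe. The multivariable label on the secondary models may mean that covariates are intended there.

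All of this stands, and it limits the point to an efficiency improvement. It does not remove the point. The strata are absent from the stated primary model, the moderator analyses do not substitute for them, and adjustment costs almost nothing even if it gains nothing.

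**Conclusion.** The omission is established from the text; its consequence is conditional. Leaving out the strata is conservative to the extent that they predict change in PHQ-9, and has no effect on the arm-by-time term if they affect only its level. For an assumed slope R² of 0 to 0.10, the unadjusted SE is 0 to 5.4% wider than it need be. Type I error runs from about 5% down to about 4% under blocked allocation, and stays closer to 5% if allocation within strata is unblocked. These sizes rest on assumed values of R², assumed block size and stratum prevalences, and complete data.

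If the primary comparison is instead PHQ-9 at two months, stratum effects on level could matter directly, and the relevant R² would be the share of variance in that score. The SAP's statement of the primary outcome and its primary model should therefore be aligned before the size is judged. This is a worthwhile, near-free improvement, not a threat to validity.

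**What to change.** 1. Settle the age factor. The stated split leaves age 46 unassigned, and the cut is described as an estimate. Record the cut-point actually used by the randomisation system, and state the allocation method and block size.
2. In the SAP's Analysis of primary outcome and the matching protocol section, add the three factors, coded as used at randomisation, as level-2 predictors of both the intercept and the time slope. Use main effects rather than all eight cells, since 90/8 is only about 11 people per stratum.
3. If a two-month contrast is the primary comparison, enter the same three factors as covariates in it.
4. Name the same factors in the secondary-outcome models and in the imputation model, so that the imputation contains every term in the analysis model. For binary outcomes, note that the odds ratio is then conditional on the strata.
5. Keep the moderator analyses as a separate exploratory step.

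The cost is SAP wording and six extra parameters, three on the intercept and three on the slope. The loss of degrees of freedom is negligible: for the slope contrast, 88 become 85 and the critical value moves from 1.987 to 1.988. With no stratum effect on slope, the simulated unadjusted SE was 0.999 of the adjusted one, so adjusting needlessly costs about 0.1%.

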While promising research is underway to improve engagement/adherence to existing depression EBTs and to develop new treatments, other approaches should be considered. One of these is an existing EBT with a strong research pedigree but has low adoption in clinical care: bright light therapy (BLT), most often administered via a “light box.” BLT was developed out of basic science regarding seasonal affective disorder (SAD). For many years, BLT has been viewed as an appropriate treatment for SAD but not for non-SAD depression. However, recent trials and meta-analyses reveal that BLT yields medium to high clinical benefit for non-SAD depression as well as SAD, as both monotherapy or as an adjunct to ADs. BLT has several advantages over existing pharmacotherapy or psychotherapy. First, at a typical light box purchase price of \$70 to \$110 it is relatively affordable, and many insurance plans reimburse patients for the purchase cost. Second, BLT is hypothesized to work via a different mechanism than pharmacotherapy or psychotherapies, and evidence points to additional benefit when BLT augments other EBTs. Third, properly educated and motivated patients can self-administer BLT at home, alleviating barriers of travel burden and limited access to care—telehealth issues that have been highlighted during the present pandemic. Finally, contraindications are minimal (e.g., skin/eye photosensitivity), side effects are typically minor/transient, and antidepressant action is rapid (within 1-2 weeks). Despite these advantages adoption/promotion of BLT is low, even when patients are not engaged in other depression EBT. This represents a care gap that may be addressed in part with BLT.

Given that BLT has established medium-large efficacy, what is the next step? A large pragmatic effectiveness trial is a logical progression of research: to examine benefit of a deployment-ready BLT approach when delivered to complex real-world patients in an active health care system setting, against a background of other usual care. This trial will evaluate BLT effectiveness with little of the “scaffolding” typical of highly controlled efficacy trials. This R34 pilot will prepare for a future, fully-powered effectiveness trial.

4. Study Design

This is a three-arm randomized controlled trial (RCT), with treatment as usual (TAU; i.e., usual care) underlying all study arms. Following a 2-stage eligibility screening and baseline assessment, patients will be randomly assigned to:

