- Arm 1: Treatment as Usual (TAU) control: A “usual care” control group (e.g., antidepressants, watchful waiting, psychosocial therapy, or no treatment, all determined by the participant in consultation with their TAU providers). All TAU will be recorded for all participants in all study conditions; or
- Arm 2: TAU + Minimal BLT Encouragement: TAU plus two minimal communications (mailed letter, secure EHR message, email, or text) identifying BLT as a promising treatment and outlining steps for participants to self-initiate. Arm 2 will not include any phone coaching or adherence promotion.
- Arm 3: TAU + Enhanced BLT Encouragement + Adherence Promotion + MI: TAU plus 2-6 brief calls to encourage BLT use, advise on purchase of a light box (LB) that meets all ideal technical

standards, assist with obtaining compensation for LB purchase, educate for correct LB use, and provide motivational interviewing (MI) as needed to promote adherence.

Outcomes will be assessed at baseline, 2, 4, and 6 months. The acute intervention period will be for 2 months. The primary outcome will be scores on the Patient Health Questionnaire-9 (PHQ-9), selected as representative of how depression is assessed in many usual care settings, consistent with effectiveness research principles.

5. Study Population

a. Number of Subjects

We will enroll 90 to 100 participants.

b. Inclusion and Exclusion Criteria

Potentially eligible individuals will be screened at two points in the recruitment phase: 1) preliminary identification of likely participants via a search of KPNW electronic health record (EHR) and 2) phone or online screening survey.

EHR inclusion criteria:

- Age 18-69 years, inclusive, and
- New episode of unipolar depression within the last month, defined as: New ICD-10 diagnosis of SAD or unipolar depression (i.e., major depression, minor depression, depression not otherwise specified, and/or adjustment disorder with depressed mood) AND usual care administration of the PHQ-9 depression scale in the last 30 days, with a total score of 10 or higher, and
- Participant must have a kp.org MyChart account, with evidence of use in the last 12 months.

EHR exclusion criteria:

- Chronic depression: ICD-10 diagnosis of SAD or unipolar depression in the 6 months prior to case-identification;
- Elevated PHQ-9 (score of 10 or higher) in the 6 months prior to case identification.

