## Power analysis, sample size

The R34 pilot funding cap limits us to a feasibility sample that is insufficient for an adequately powered test of the hypothesis. Nonetheless, we provide an estimate of the statistical power obtained from this sample of 90 participants. Meta-analyses suggest an overall effect size for BLT of  $d=0.84$ [14]. We conservatively estimate the effect size likely to be obtained in this pilot trial as lower than reported in meta-analyses because this is a real-world effectiveness population; even with Arm 3 adherence promotion BLT adherence is likely to be lower than in efficacy trials, leading to lower clinical benefit. Assuming a retained sample size of  $N=81$  at the final 6-month assessment, we conducted power analysis for the HLM of the primary outcome (using SAS version 9.4) to determine the minimum detectable effect size. At a two-tailed alpha level of .05 and conservatively assuming an autocorrelation of .70, we would have 80% power to detect a Cohen's  $d$  for the time by arm effect as small as 0.39 for the contrast between active intervention arms (Arms 2 and 3) and TAU, and as small as 0.55 for contrasts between individual arms; both estimates are medium effects.

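### The primary model tests a slope over months 0 to 6 with no baseline PHQ-9 adjustment, while the SAP's primary outcome is PHQ-9 at month 2; a baseline-adjusted, categorical-visit month-2 contrast would match it

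*SAP*

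**What the plan says.** The SAP (Rationale and research questions) states: "Our primary clinical outcome is the PHQ-9 at post-acute treatment (2 months follow-up". Its Hypotheses section predicts, for the two BLT arms combined, "larger reductions in PHQ-9 at post-acute treatment than the TAU control arm", and makes the enhanced-versus-minimal prediction at the same time point. The Protocol (section 4) schedules assessments at baseline and months 2, 4 and 6, and adds: "The acute intervention period will be for 2 months".

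The SAP (Analysis of primary outcome) and the matching text in Protocol section 6a specify a two-level growth model. Time is the level-1 predictor. The arm dummy enters at level 2 "as the predictor variable for both the random effects of the intercept and slope for time", and the test is the arm coefficient on the slope. No other level-2 term is named, and neither document says how time is coded. The SAP carries the same model to the continuous secondary outcomes.

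Baseline is measured before allocation (Protocol section 4: "Following a 2-stage eligibility screening and baseline assessment, patients will be randomly assigned to"). In the primary model it serves only as the time-0 outcome. As a predictor, baseline PHQ-9 appears only as a dichotomised exploratory moderator. For the insomnia mediator, by contrast, the SAP says "we will regress post-acute treatment ISI on baseline ISI and a randomization condition indicator".

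**The concern.** The primary outcome is a score at one visit; the primary test is a rate of change over six months. The two agree only if the arm difference grows in a straight line from baseline to month 6. The Protocol gives a reason to doubt that: its background section says of BLT that "antidepressant action is rapid (within 1-2 weeks". An early effect that then holds is poorly described by one slope.

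Baseline PHQ-9 is also available to tighten the month-2 estimate and is not used for that. The pilot promises a cautious effect estimate with a confidence interval, from analyses that mirror the future trial (SAP Introduction, Aim 2). A model choice made here is therefore likely to carry forward.

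**Working it through.** **Inputs.** Visits 0, 2, 4, 6 (Protocol section 4). Retained N = 81 at month 6, two-sided alpha 0.05, 80% power, and "conservatively assuming an autocorrelation of .70" (SAP, Power analysis). Allocation is 1:1:1 (Protocol, Randomization), so 27 per arm, or 54 vs 27 for Arms 2+3 against Arm 1. The documents give no PHQ-9 SD, so k, the month-2 SD divided by the baseline SD, is an assumption, taken from 1.0 to 2.0. The PHQ-9 entry floor of 10 makes k above 1 plausible.

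**1. The plan's own figures.** Minimum detectable d = (1.96 + 0.84) × √[f(1/n1 + 1/n2)].
- Baseline-adjusted, f = 1 − 0.70² = 0.51. For 27 vs 27: 2.80 × √0.0378 = 0.545, or 0.555 with t critical values. The stated 0.55 is reproduced.
- Unadjusted change, f = 2(1 − 0.70) = 0.60. For 27 vs 27: 0.59.
- For 54 vs 27 with f = 0.51: 0.47, not the stated 0.39. That figure appears only with 54 in each group (0.385).

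The 0.55 is consistent with a baseline-adjusted factor but does not prove it. The SAS program is not in the documents, and a six-month slope under equal correlation gives a nearby 0.56.

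**2. Effect shape.** Assume straight-line time from 0 at baseline, complete data, and a true arm difference of 0, 1, 1, 1 at the four visits.
- Equal correlation: slope = [(−3)(0) + (−1)(1) + (1)(1) + (3)(1)]/20 = 0.15. Intercept difference = 0.75 − 3 × 0.15 = 0.30. Fitted month-2 difference = 0.30 + 0.30 = 0.60; 2 × slope = 0.30.
- AR(1) with 0.70 between adjacent visits: 0.12 + 0.33 = 0.45; 2 × slope = 0.33.
- Arm dropped from the intercept (equal correlation): 0.33.
- Categorical visit, baseline free or constrained: 1.00.

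For an effect that fades (0, 1, 0.75, 0.5; equal correlation), the planned line gives 0.50, the line without arm on the intercept 0.16, and categorical visit 1.00.

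**3. Precision of the month-2 contrast.** The comparator is unadjusted month-2 change from baseline. With baseline SD 1, change has variance factor 1 + k² − 1.4k and the adjusted contrast has 0.51k². Estimating the baseline coefficient multiplies the latter by 1 + 1/(81 − 4) = 78/77.

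| k | change | adjusted | ratio | net ratio, N = 81 |
|---|---|---|---|---|
| 1.0 | 0.600 | 0.510 | 0.850 | 0.861 |
| 1.1 | 0.670 | 0.617 | 0.921 | 0.933 |
| 1.2 | 0.760 | 0.734 | 0.966 | 0.979 |
| 1.43 | 1.043 | 1.043 | 1.000 | 1.013 |
| 2.0 | 2.200 | 2.040 | 0.927 | 0.939 |

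Simulation (40,000 trials, N = 81) agrees: 14.1% saved at k = 1, 1.9% at 1.2, and 1.1% lost at 1.43. At k = 1 the large-sample 95% half-width goes from 0.36 to 0.33 SD (54 vs 27) and from 0.41 to 0.38 SD (27 vs 27). At equal SD the large-sample gain is (1 − ρ)/2: 25% at ρ = 0.5, 15% at 0.7 and 10% at 0.8.

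**4. Against the planned model** (54 vs 27, k = 1). The adjusted month-2 contrast has variance 0.0283. Twice the slope has 0.0033 (equal correlation) or 0.0081 (AR(1)), so the contrast has about 8.5 or 3.5 times the variance. The planned model's own fitted month-2 difference, intercept plus 2 × slope, has 0.0439 or 0.0384; against that, the contrast is 35% or 26% lower.

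**The case against.** The strongest objection is that precision does not justify the switch. The planned estimator is a slope using all four visits, and the 14% is not a gain over it; step 4 shows the slope is far more precise. That stands. But the slope's small variance is bought by assuming linear change, and under the early, sustained effect it reports about 0.3 of the month-2 difference. The ground for the fix is the match to the named outcome; precision is secondary.

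Other parts also stand:
- A growth model already uses baseline as its first outcome, so the contrast with the mediator regression is suggestive rather than an inconsistency.
- Adding the randomisation factors brings no variance gain worth claiming. In 20,000 simulated trials per case with stratified blocks and baseline already adjusted, the variance ratio was 1.004 and 1.001 when the strata explained 5% and 10% of PHQ-9 variance.
- The stakes are modest in a pilot that repeatedly calls itself underpowered.

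A reader might infer that the planned model is invalid, or that arm should simply be taken off the intercept. The documents support neither. Randomisation keeps the slope test valid. With straight-line time, the intercept is the fitted line at time 0, not the observed baseline mean, so removing arm from it worsens the month-2 prediction in step 2.

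**Conclusion.** The concern holds as a mismatch between a month-2 outcome and a six-month slope test, with an unused opportunity to adjust for baseline. It is worth considering and is not an error that invalidates the plan.

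The shortfall figures (0.60 or 0.45 for the fitted difference, about 0.30 to 0.33 for 2 × slope) rest on straight-line time and a full effect from month 2. The SAP states neither; if the arm difference grows linearly, the slope model is correct and more precise. The variance saving rests on ρ = 0.70 and on an SD ratio that the documents do not give. It ranges from about 14% net to a loss of about 1%, with some gain returning at larger ratios (about 6% at 2.0).

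A reader might infer that adjustment would improve on the stated power. It should not be credited that way: the 0.55 is already consistent with a baseline-adjusted variance factor. The omission and the arithmetic are firm; the size of the benefit is conditional.

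**What to change.** For PHQ-9 and the continuous secondary outcomes, model the scores at months 2, 4 and 6 with visit as a categorical factor, arm by visit, and the baseline score with a baseline-by-visit term. A constrained-baseline model with categorical time is an equivalent choice. Name the month-2 arm contrast as the primary estimate. Include the three randomisation factors for consistency with the stratified design, without claiming a variance gain. Make the same change in the Protocol's data analysis section. If a slope is kept as a supporting analysis, state how time is coded and leave arm on the intercept.

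The cost is one or two sentences in the SAP and no new data. The model grows from 4 fixed effects to 12 for the pooled contrast, or 15 with three arms, counting the randomisation factors. If month-2 spread is about 1.43 times baseline, adjustment loses about 1 to 2% of variance. If change really is linear, the month-2 interval will be wider than the one the slope would give.
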